**PHYSICAL FRAILTY ASSESSMENT**

1	Self-reported weight loss (not due to dieting or fasting) in preceding 12 mo $\geq 4.5$ kg	YES / NO																											
2	Grip strength measured using dynamometer	
  
 Sex	BMI	Grip strength cutoff (kg)	
   
 Male	<math>\leq 24</math>	<math>\leq 29</math>	
 
 	24.1 - 26	<math>\leq 30</math>	
 
 	26.1 - 28	<math>\leq 30</math>	
 
 	<math>> 28</math>	<math>\leq 32</math>	
 
 Female	<math>\leq 23</math>	<math>\leq 17</math>	
 
 	23.1 - 26	<math>\leq 17.3</math>	
 
 	26.1 - 29	<math>\leq 18</math>	
 
 	<math>> 29</math>	<math>\leq 21</math>	
  
 
Is grip strength below cutoff for sex/age?
	Sex	BMI	Grip strength cutoff (kg)	Male	$\leq 24$	$\leq 29$		24.1 - 26	$\leq 30$		26.1 - 28	$\leq 30$		$> 28$	$\leq 32$	Female	$\leq 23$	$\leq 17$		23.1 - 26	$\leq 17.3$		26.1 - 29	$\leq 18$		$> 29$	$\leq 21$
Sex	BMI	Grip strength cutoff (kg)																											
Male	$\leq 24$	$\leq 29$																											
	24.1 - 26	$\leq 30$																											
	26.1 - 28	$\leq 30$																											
	$> 28$	$\leq 32$																											
Female	$\leq 23$	$\leq 17$																											
	23.1 - 26	$\leq 17.3$																											
	26.1 - 29	$\leq 18$																											
	$> 29$	$\leq 21$																											
3a	Ask participant "How often over the past week have you felt that everything you did was an effort?"	YES / NO																											
3b	Ask participant "How often over the past week have you felt that you could not get "going"?"	Score 2 or 3																											
4	Time to walk 15ft (4.57m) $\leq$ slowest 20% adjusted for gender and standing height	
  
 Sex	Height (cm)	Cutoff time to walk 15ft	
   
 Male	<math>\leq 173</math>	<math>\geq 7</math> sec	
 
 	<math>> 173</math>	<math>\geq 6</math> sec	
 
 Female	<math>\leq 159</math>	<math>\geq 7</math> sec	
 
 	<math>> 159</math>	<math>\geq 6</math> sec	
  
 
Is time to walk greater than cutoff for sex/height?
	Sex	Height (cm)	Cutoff time to walk 15ft	Male	$\leq 173$	$\geq 7$ sec		$> 173$	$\geq 6$ sec	Female	$\leq 159$	$\geq 7$ sec		$> 159$	$\geq 6$ sec												
Sex	Height (cm)	Cutoff time to walk 15ft																											
Male	$\leq 173$	$\geq 7$ sec																											
	$> 173$	$\geq 6$ sec																											
Female	$\leq 159$	$\geq 7$ sec																											
	$> 159$	$\geq 6$ sec																											
5	IPAQ Short Version Activity Level _____ MET-min	
  
 Kcal		Cutoff		
 
 [kcal = MET-min x (weight kg / 60)]	Men	<math>< 383</math> kcal	Is activity level (kcal) below cutoff for gender?	
 
 	Women	<math>< 270</math> kcal	YES / NO	
  
	Kcal		Cutoff		[kcal = MET-min x (weight kg / 60)]	Men	$< 383$ kcal	Is activity level (kcal) below cutoff for gender?		Women	$< 270$ kcal	YES / NO															
Kcal		Cutoff																											
[kcal = MET-min x (weight kg / 60)]	Men	$< 383$ kcal	Is activity level (kcal) below cutoff for gender?																										
	Women	$< 270$ kcal	YES / NO																										
		TOTAL NUMBER OF "YES" / 5																											
		If 1 or 2 YES      Include																											
		If 0 or >2 YES EXCLUDE																											

**COGNITIVE FRAILTY ASSESSMENT**

1	MMSE Raw Score = _____ / 30	Age-Adjusted Score $\leq$ 26	YES / NO
MMSE Age-adjusted Score = _____ / 30			
2	Hopkins Verbal Learning Test (HVLT)	HVLT total recall score $\leq$ 24	YES / NO
HVLT total recall score = _____ / 36			
TOTAL NUMBER OF “YES”			/ 2
		If 0 YES	Include
		If 1 or 2 YES	EXCLUDE

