#### **INCLUSION CRITERIA**

---

1. Age: over 60 yrs
2. Familiar with use of smartphones and/or tablet computers
3. Have access to WiFi connection and existing internet data plan and provider
4. Able to stand and walk unassisted
5. Free of significant cognitive impairment (age-corrected MMSE  $\geq 24$ ) (Table 4)
6. Free of clinically significant mood disturbance (HADS-Anxiety  $<15$ ; HADS-depression  $< 15$ ) (Table 4)
7. Free of any acute or unstable medical conditions
8. Meet criteria for pre-frail status (Table 2)
9. Able to understand directions and participate in the protocol
10. Able to sign informed consent

---

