**Table 4: Exclusion criteria for clinically significant deficits in Cognitive and Psychological function**

Clinical sign/symptom		Measure	Cutoff values	
COGNITIVE DOMAIN	Must NOT meet 1 or more of the EXCLUSION CRITERIA		INCLUSION CRITERIA	EXCLUSION CRITERIA
1. Evidence of lowered general cognitive function	Mini Mental State Examination test (MMSE) screens for deficits across several cognitive functions.	Age-adjusted MMSE 
 
• 24-30 (no cognitive impairment)
 
	Age-adjusted MMSE score 
 
• 18-23 = MCI
 
• 0-17 = severe clinical deficit
 
	
2. Evidence of lower than age-appropriate learning and recall of verbal information	Hopkins Verbal Learning Test (HVLT) is a brief test of verbal list learning and memory. Comprises 12 words, organized into three semantic categories, and presented over three consecutive learning trials.	HVLT-total recall score 
 
• Score <math>\geq 25</math>
 
	HVLT-total recall score 
 
• Score <math>\leq 24</math>
 
	
PSYCHOLOGICAL DOMAIN	Must NOT meet any EXCLUSION CRITERIA		INCLUSION CRITERIA	EXCLUSION CRITERIA
1. Increased levels of anxiety and/or lowered mood experienced over the preceding week	HADS – Hospital and Depression Scale, a 14-item scale to which participant indicates degree of agreement/frequency of experience in previous week on a 4 point scale. Seven of the items relate to anxiety and seven relate to depression.	Scores are computed separately for the Anxiety scale (7 items – HADS-a) and the Depression scale (7 items – HADS-d): 
 
0-7 = normal mood
 
8-10 = mild symptoms
 
11-14 = moderate symptoms
 
	
 
• Scores <math>\geq 15</math> - HADS-d and/or
 
• Scores <math>\geq 15</math> - HADS-a
 
	

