### 3.3 Screening Failures

Screen Failures are defined as participants who sign a Screening Participant Informed Consent Form (PICF-Screen) for My-AHA study but are not subsequently randomized and who do not enter the RCT. Participants who are Screen Failures may be rescreened once only after approval by the study Medical Supervisor (University of Torino, Italy).

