## 6.2 Screening questionnaire

Persons expressing an interest in participating in the My-AHA RCT will undergo formal screening to ensure that they meet inclusion criteria and do not meet any of the identified exclusion criteria (see Section 3 Participant Screening, Table 1, Table 2, Table 3, Table 4). A standard questionnaire for participant screening will be used (Appendix 4) along with standard forms for the MMSE, HVLT, IPAQ, and HADS which will be administered to confirm each participant meets pre-frailty criteria for inclusion in the RCT. It is estimated that the screening process will take a maximum of 60 minutes to complete.

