## 6.7 Cognitive assessment

### 6.7.1 Mini-Mental State Examination (MMSE)

The MMSE is an 11-item brief screening assessment of basic cognitive functions  (Appendix 14). The MMSE is a clinical test, and will be administered by a trained and experienced researcher under the supervision of A/[name], APHRA registered Psychologist endorsed for practice as a Clinical Neuropsychologist.

The 11 items on the MMSE assess:

1. Orientation to time
2. Orientation to place
3. Registration of 3 objects
4. Attention and calculation
5. Recall of 3 objects
6. Language and praxis

Scores on the MMSE range from 0-30, and are corrected for level of education.

Abnormal cutoff scores are:

- < 24 – university/college education
- < 23 – high school education (9-12 years formal education)
- < 21 – junior high school education or less (fewer than 9 years of formal education)

[figure not shown]

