**PSYCHOLOGICAL FRAILTY ASSESSMENT**

1	HADS Anxiety Score = _____ / 21	HADS Anxiety Score $\geq$ 15	YES / NO
2	HADS Depression Score = _____ / 21		
	HADS Depression Score $\geq$ 15		
TOTAL NUMBER OF “YES”			/ 2
		If 0 YES	Include
		If 1 or 2 YES	EXCLUDE

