### **Interpretation of the MMSE**

Method	Score	Interpretation
Single Cutoff	<24	Abnormal
Range	<21	Increased odds of dementia
	>25	Decreased odds of dementia
Education	21	Abnormal for 8 th grade education
	<23	Abnormal for high school education
	<24	Abnormal for college education
Severity	24-30	No cognitive impairment
	18-23	Mild cognitive impairment
	0-17	Severe cognitive impairment

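### The Appendix 4 screening form excludes an age-adjusted MMSE of 26 or less, while Tables 1 and 4 admit 24 to 30, so scores of 24, 25 and 26 get opposite eligibility decisions

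*Protocol*

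**What the plan says.** - **Table 1, criterion 5** (Section 3.1) requires volunteers to be "Free of significant cognitive impairment (age-corrected MMSE" of at least 24), and refers to Table 4.
- **Table 4** (Section 3.2) lists "24-30 (no cognitive impairment") as the inclusion band on the age-adjusted score. It lists 18–23 and 0–17 as exclusion bands.
- **Appendix 4, Cognitive Frailty Assessment, item 1** asks for the raw and the age-adjusted MMSE and marks YES at "Age-Adjusted Score $\leq$ 26". Item 2 marks YES for an HVLT total recall of 24 or less. No YES means include; one or two YES means exclude.
- **Section 6.2** makes this form the operative one: "A standard questionnaire for participant screening will be used (Appendix 4").
- **Section 3.3** limits a second attempt: "Participants who are Screen Failures may be rescreened once only after approval by the study Medical Supervisor".
- **The MMSE interpretation sheet** bound into the screening package labels 24–30 "No cognitive impairment" in its severity row and uses below 24 as its single cut-off for abnormal.
- **Section 6.7.1** says that MMSE scores "are corrected for level of education" and gives abnormal cut-offs of below 24, below 23 and below 21 by schooling.

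**The concern.** An eligibility threshold is stated consistently in two tables and contradicted on the form that applies them. For a score of 24, 25 or 26, site staff cannot follow both. If they follow the form, volunteers who satisfy the stated MMSE criterion are lost from a planned sample of 50 (Section 2.1; 25 per arm in Section 4). The people enrolled then differ from the population the protocol describes. If sites resolve the conflict differently, they enrol different populations into data that Section 10.2 says will be combined. Rescreening offers little relief: it is allowed once, needs approval, and would apply the same line again if the same form is used.

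**Working it through.** No sample-size or power figure is involved. The check is a comparison of the two rules over every whole-number MMSE score from 0 to 30.

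**Inputs**
- Tables 1 and 4: eligible if the age-adjusted score is 24 or more.
- Appendix 4, cognitive item 1: YES if the age-adjusted score is 26 or less. One YES excludes, so the item is passed only at 27 or more.

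**Result**

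| Age-adjusted MMSE | Tables 1 and 4 | Appendix 4 form |
|---|---|---|
| 0–23 | exclude | exclude |
| 24, 25, 26 | include | exclude |
| 27–30 | include | include |

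- The tables admit 24 to 30, which is 30 − 24 + 1 = 7 scores.
- The form admits 27 to 30, which is 30 − 27 + 1 = 4 scores.
- Scores admitted by the tables but failed by the form: 24, 25 and 26 (7 − 4 = 3).
- Scores admitted by the form but excluded by the tables: none.
- If the form's line read 23 or less, the two rules would agree at every score from 0 to 30. This locates the discrepancy; it does not show which limit was intended.

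**Is the form stricter by design?** The form's other cognitive and psychological cut-offs can be set against Table 4:

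| Item | Form excludes at | Table 4 excludes at | Agree? |
|---|---|---|---|
| MMSE | 26 or less | 23 or less | no |
| HVLT total recall | 24 or less | 24 or less | yes |
| HADS-Anxiety | 15 or more ("HADS Anxiety Score $\geq$ 15") | 15 or more | yes |
| HADS-Depression | 15 or more | 15 or more | yes |

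Three of the four match, and only the MMSE line departs. No text announces a tighter MMSE limit for screening.

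**Is it raw against adjusted?** No. Tables 1 and 4 and the form all apply the limit to the age-adjusted score, and the form has a separate field for the raw score.

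**Does the interpretation sheet support 26?** No. It has no boundary between 26 and 27; its nearest row is above 25, for decreased odds of dementia. A score of 26 falls on the favourable side of every row.

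**Secondary point.** Tables 1 and 4 and the form call the score age-adjusted, whereas Section 6.7.1 describes a correction for education. The cut-offs differ as well as the wording. Under Section 6.7.1 a score of 23 is not abnormal for someone with high-school education, and 21 to 23 is not abnormal for someone with fewer than nine years of schooling, yet Table 4 excludes 18–23. Section 6.7.1 presents these as abnormality cut-offs rather than entry limits, and none of them yields 26.

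**The case against.** The contradiction itself has no good rebuttal: the lines are current and intact, and nothing in the protocol justifies a stricter form. The fair objections concern its weight and framing.

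- **Whole-number scores.** The protocol does not say how the age adjustment is made. If it can give fractions, the conflict is the interval from 24 to 26 rather than three scores. The form and Table 4 both work in whole numbers out of 30, so three scores is the natural reading, but it is an assumption.
- **Limited harm.** Nobody is wrongly admitted on this line, and the comparison between arms is not biased. Some volunteers scoring 24 to 26 would fail on the HVLT or another criterion anyway. This stands, and it keeps the point from being more serious.
- **The tables could be read as governing.** Sections 2.1 and 6.2 say that screening is to ensure the tabulated criteria are met. That gives an investigator grounds to override the form, but Section 6.2 prescribes the form in the same paragraph, so the conflict remains.
- **The interpretation sheet is weak corroboration.** It offers several methods side by side, and its severity bands are the same as those in Table 4. This is fair; the finding rests on Tables 1 and 4 against Appendix 4 and does not need the sheet.
- **The figure of 50.** Section 2.1 ties it to one region, while other sections describe several sites. It is the only sample size the protocol states and is used here only as context.

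**Conclusion.** The concern holds. Tables 1 and 4 set the MMSE limit at 24, and the prescribed screening form excludes up to 26. On whole-number scores the conflict is exactly 24, 25 and 26, and the form's population (27–30) is a strict subset of the tables' (24–30). The consequences are avoidable loss of volunteers who meet the stated MMSE criterion and a misdescribed population; the between-arm comparison is not biased. The number of people affected cannot be estimated, since the protocol gives no MMSE distribution, and anyone scoring 24 to 26 must still meet every other criterion. This should be fixed, but it does not threaten the validity of the comparison.

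**What to change.** - Reconcile Table 1 criterion 5, Table 4 and the Appendix 4 MMSE line to one threshold. Either bring the form into line with the tables, or amend both tables if the stricter limit was intended. The choice is the sponsor's and should be recorded.
- State which correction defines the MMSE score used for eligibility, and reconcile Section 6.7.1, including its education-specific cut-offs, with the tables and the form.
- If screening has begun, review anyone screen-failed solely on an age-adjusted MMSE of 24 to 26 against the reconciled rule.

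The cost is one line on the form, or one criterion in Table 1 and one row in Table 4, plus a short revision of Section 6.7.1. Section 11.1.2 requires ethics committee approval of the change before it is implemented. Any review of screen failures is confined to those recorded on this item alone.

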**PSYCHOLOGICAL FRAILTY ASSESSMENT**

1	HADS Anxiety Score = _____ / 21	HADS Anxiety Score $\geq$ 15	YES / NO
2	HADS Depression Score = _____ / 21		
	HADS Depression Score $\geq$ 15		
TOTAL NUMBER OF “YES”			/ 2
		If 0 YES	Include
		If 1 or 2 YES	EXCLUDE

# INTERNATIONAL PHYSICAL ACTIVITY QUESTIONNAIRE

## (IPAQ)

**PARTICIPANT SCREEN NUMBER:** \_\_\_\_\_

**STUDY SITE:** \_\_\_\_\_

**TEST PHASE:** Screening

We are interested in finding out about the kinds of physical activities that people do as part of their everyday lives. The questions will ask you about the time you spent being physically active in the **last 7 days**. Please answer each question even if you do not consider yourself to be an active person. Please think about the activities you do at work, as part of your house and yard work, to get from place to place, and in your spare time for recreation, exercise or sport.

Think about all the **vigorous** activities that you did in the **last 7 days**. **Vigorous** physical activities refer to activities that take hard physical effort and make you breathe much harder than normal. Think *only* about those physical activities that you did for at least 10 minutes at a time.

1. During the **last 7 days**, on how many days did you do **vigorous** physical activities like heavy lifting, digging, aerobics, or fast bicycling?

\_\_\_\_\_ **days per week**

No vigorous physical activities

→ **Skip to question 3**

2. How much time did you usually spend doing **vigorous** physical activities on one of those days?

\_\_\_\_\_ **hours per day**

\_\_\_\_\_ **minutes per day**

Don't know/Not sure

Think about all the **moderate** activities that you did in the **last 7 days**. **Moderate** activities refer to activities that take moderate physical effort and make you breathe somewhat harder than normal. Think only about those physical activities that you did for at least 10 minutes at a time.

3. During the **last 7 days**, on how many days did you do **moderate** physical activities like carrying light loads, bicycling at a regular pace, or doubles tennis? Do not include walking.

\_\_\_\_\_ **days per week**

No moderate physical activities

→ **Skip to question 5**

4. How much time did you usually spend doing **moderate** physical activities on one of those days?

\_\_\_\_\_ **hours per day**

\_\_\_\_\_ **minutes per day**

Don't know/Not sure

# INTERNATIONAL PHYSICAL ACTIVITY QUESTIONNAIRE

## (IPAQ)

Think about the time you spent **walking** in the **last 7 days**. This includes at work and at home, walking to travel from place to place, and any other walking that you have done solely for recreation, sport, exercise, or leisure.

5. During the **last 7 days**, on how many days did you **walk** for at least 10 minutes at a time?

\_\_\_\_\_ **days per week**

No walking      → **Skip to question 7**

1. How much time did you usually spend **walking** on one of those days?

\_\_\_\_\_ **hours per day**

\_\_\_\_\_ **minutes per day**

Don't know/Not sure

The last question is about the time you spent **sitting** on weekdays during the **last 7 days**. Include time spent at work, at home, while doing course work and during leisure time. This may include time spent sitting at a desk, visiting friends, reading, or sitting or lying down to watch television.

2. During the **last 7 days**, how much time did you spend **sitting** on a **week day**?

\_\_\_\_\_ **hours per day**

\_\_\_\_\_ **minutes per day**

Don't know/Not sure

**This is the end of the questionnaire, thank you for participating.**

[figure not shown]
## Mini-Mental State Examination (MMSE)

Patient's Name: \_\_\_\_\_ Date: \_\_\_\_\_

**Instructions:** Ask the questions in the order listed. Score one point for each correct response within each question or activity.

Maximum Score	Patient's Score	Questions
5		"What is the year? Season? Date? Day of the week? Month?"
5		"Where are we now? State? County? Town/city? Hospital? Floor?"
3		The examiner names three unrelated objects clearly and slowly, then asks the patient to name all three of them. The patient's response is used for scoring. The examiner repeats them until patient learns all of them, if possible. Number of trials: _____
5		"I would like you to count backward from 100 by sevens." (93, 86, 79, 72, 65, ...) Stop after five answers. Alternative: "Spell WORLD backwards." (D-L-R-O-W)
3		"Earlier I told you the names of three things. Can you tell me what those were?"
2		Show the patient two simple objects, such as a wristwatch and a pencil, and ask the patient to name them.
1		"Repeat the phrase: 'No ifs, ands, or buts.'"
3		"Take the paper in your right hand, fold it in half, and put it on the floor." (The examiner gives the patient a piece of blank paper.)
1		"Please read this and do what it says." (Written instruction is "Close your eyes.")
1		"Make up and write a sentence about anything." (This sentence must contain a noun and a verb.)
1		"Please copy this picture." (The examiner gives the patient a blank piece of paper and asks him/her to draw the symbol below. All 10 angles must be present and two must intersect.)
30		TOTAL

(Adapted from Rovner & Folstein, 1987)

1

Source: [www.medicine.uiowa.edu/igec/tools/cognitive/MMSE.pdf](http://www.medicine.uiowa.edu/igec/tools/cognitive/MMSE.pdf)

Provided by NHCQF, 0106-410

### **Instructions for administration and scoring of the MMSE**

#### **Orientation (10 points):**

- Ask for the date. Then specifically ask for parts omitted (e.g., "Can you also tell me what season it is?"). One point for each correct answer.
- Ask in turn, "Can you tell me the name of this hospital (town, county, etc.)?" One point for each correct answer.

#### **Registration (3 points):**

- Say the names of three unrelated objects clearly and slowly, allowing approximately one second for each. After you have said all three, ask the patient to repeat them. The number of objects the patient names correctly upon the first repetition determines the score (0-3). If the patient does not repeat all three objects the first time, continue saying the names until the patient is able to repeat all three items, up to six trials. Record the number of trials it takes for the patient to learn the words. If the patient does not eventually learn all three, recall cannot be meaningfully tested.
- After completing this task, tell the patient, "Try to remember the words, as I will ask for them in a little while."

#### **Attention and Calculation (5 points):**

- Ask the patient to begin with 100 and count backward by sevens. Stop after five subtractions (93, 86, 79, 72, 65). Score the total number of correct answers.
- If the patient cannot or will not perform the subtraction task, ask the patient to spell the word "world" backwards. The score is the number of letters in correct order (e.g., dlrow=5, dlrow=3).

#### **Recall (3 points):**

- Ask the patient if he or she can recall the three words you previously asked him or her to remember. Score the total number of correct answers (0-3).

#### **Language and Praxis (9 points):**

- Naming:** Show the patient a wrist watch and ask the patient what it is. Repeat with a pencil. Score one point for each correct naming (0-2).
- Repetition:** Ask the patient to repeat the sentence after you ("No ifs, ands, or buts."). Allow only one trial. Score 0 or 1.
- 3-Stage Command:** Give the patient a piece of blank paper and say, "Take this paper in your right hand, fold it in half, and put it on the floor." Score one point for each part of the command correctly executed.
- Reading:** On a blank piece of paper print the sentence, "Close your eyes," in letters large enough for the patient to see clearly. Ask the patient to read the sentence and do what it says. Score one point only if the patient actually closes his or her eyes. This is not a test of memory, so you may prompt the patient to "do what it says" after the patient reads the sentence.
- Writing:** Give the patient a blank piece of paper and ask him or her to write a sentence for you. Do not dictate a sentence; it should be written spontaneously. The sentence must contain a subject and a verb and make sense. Correct grammar and punctuation are not necessary.
- Copying:** Show the patient the picture of two intersecting pentagons and ask the patient to copy the figure exactly as it is. All ten angles must be present and two must intersect to score one point. Ignore tremor and rotation.

(Folstein, Folstein & McHugh, 1975)

